## I. BACKGROUND AND SIGNIFICANCE

Chronic migraine (CM) is a complex, progressive headache disorder affecting approximately 1.3-2.4% of the general adult population. Onabotulinumtoxin type A (BoNTA) is considered an effective, FDA-approved, prophylactic treatment. Injections are administered at 31 sites of the head and neck, and treatment is repeated every 3 months. [2]

BoNTA is manufactured as powder that requires reconstitution with normal saline prior to injection. The manufacturer of botulinum A exotoxin (Allergan Inc) has historically encouraged reconstitution with unpreserved saline. [3] However, the use of preserved saline (i.e. bacteriostatic) is common among practitioners to lengthen the shelf life of BoNTA (Botox ®) after reconstitution.

A growing body of literature on the cosmetic use of BoNTA has suggested that preserved saline exerts a local anesthetic effect, and reduces the procedure discomfort when used in reconstitution in lieu of preservative-free saline. [3,4,5,6] However, this has never been studied in chronic migraine, and while reducing discomfort is a desirable target in all procedures, it has a special importance for the use of BoNTA in chronic migraineurs due to the numerous injection locations each session (31 sites) and the ubiquity of scalp tenderness in this population. [7] In addition, the pain during procedure is a known migraine trigger for many of these patients. In fact, one study showed that up to 5% report migraine attacks lasting more than 5 days as a side effect of BoNTA injection. [8]

## II. STUDY OBJECTIVES

We hypothesize that bacteriostatic saline (a.k.a preserved saline) produces lower procedure-related discomfort when used as a

dissolving solution for BoNTA injections in individuals with chronic migraine as opposed to using preservative-free saline.

In addition, we hypothesize that reduction of procedure-related pain during BoNTA injection will also result in reduced migraine/headache attacks in the week immediately following the procedure.

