#### D. Study Procedures

UHCC headache clinic performs 20-25 BoNTA injections a week on average. Enrollment plan is as following: on weekly basis, one of the investigators, either SH or AF, will contact all patients scheduled for BoNTA injections and explain the study's objectives and details. If the subject agrees to enroll, he/she will be assigned a study serial number and will be randomized to one of the two groups. Randomization will be done through a simulated "coin flipper" website; [www.random.org](http://www.random.org). Heads will be assigned to the preserved saline group, and tails will be assigned to the preservative-free saline group. SH and AF will keep the assignment sheet in a password-protected excel file that only they have access to.

On the day of the procedure, informed consent will be confirmed and signed. Then, each subject will receive 10-15 minute session on the appropriate use of headache diary.

Same randomizing investigator will reconstitute BoNTA vial (Allergan Inc) using one of the two identical solutions, and then hand it to the principal investigators; AZ or LM, who will be

performing the procedure using 30G 1/2' needles. AZ ,LM, and the subject will all be blinded to which solution is used for reconstitution.

Following the injections, subjects will be asked to rate procedure-related pain using verbal pain rating scale (0 to 10). They will be asked to maintain a 7-day headache diary (see supplementary). Prepaid mail envelopes will be provided to ensure the return of the diaries following their completion.

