#### **IV. DATA COLLECTION**

Collected data will include age, gender, race, ethnicity, verbal pain rating scale, headache/migraine frequency and use of headache symptomatic medications.

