#### **V. DATA ANALYSIS**

Sample size determination was calculated based on a minimally significant mean difference in verbal pain score of 1.5. To detect this difference with 90% power, alpha = .05; a total of 70 subjects (35 per group) will be required (SD=1.9). T-tests will be used to compare outcome of both groups. Statistical analysis will be carried by GB.

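### No pre-injection headache measure is described and week-1 headache is compared unadjusted; one written question plus ANCOVA is a cheap improvement that may add some power

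*Combined protocol and SAP*

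**What the plan says.** Section II states two hypotheses. The first concerns procedure-related discomfort. The second is that reducing that pain "will also result in reduced migraine/headache attacks in the week immediately following the procedure".

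Section III.D describes one headache record, kept after the injections: "They will be asked to maintain a 7-day headache diary (see supplementary". The form itself is not in the available text. Earlier on the procedure day, after consent is signed and before the vial is reconstituted, the plan provides training: "Then, each subject will receive 10-15 minute session on the appropriate use of headache diary". Allocation is made earlier still, by a simulated coin toss with no stratification: "Heads will be assigned to the preserved saline group, and tails will be assigned to the preservative-free saline group".

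Section IV reads: "Collected data will include age, gender, race, ethnicity, verbal pain rating scale, headache/migraine frequency and use of headache symptomatic medications". Headache frequency carries no time point there.

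Section V names one method and no covariate: "T-tests will be used to compare outcome of both groups". The sample size rests on the pain score only: "Sample size determination was calculated based on a minimally significant mean difference in verbal pain score of 1.5", with SD 1.9 and 35 per group.

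**The concern.** How often a person with chronic migraine has headaches before treatment may well predict how often headaches occur in the following week. If so, part of the between-subject spread in the week-1 count is predictable and can be removed from the comparison. As described, nothing in the plan does this. No baseline is recorded, allocation is not stratified, and a two-group t-test would not use a baseline even if the unseen diary form asked for one.

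What is at stake is power for the second hypothesis. The headache comparison inherits a sample size chosen for pain. The documents give no expected headache effect, and the proposed route is indirect (saline type, then pain, then attacks), so a large effect cannot be taken for granted. Timing matters too: analysis wording can be amended later, but a pre-injection answer that was never collected cannot be recovered reliably.

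**Working it through.** **1. The plan's own figure.** Inputs from Section V: difference 1.5, SD 1.9, 35 per group, and "To detect this difference with 90% power, alpha = .05". Sidedness is not stated. The two-sided noncentral-t calculation gives 90.2% power at 35 per group and 89.4% at 34, so N = 70 reproduces. A one-sided test would need about 28 per group, which does not match. Two-sided .05 is used below.

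**2. What that N gives the headache comparison.** With no headache SD in the documents, effects are in SD units. At 35 per group the t-test has 90% power for 0.786 SD and 80% power for 0.679 SD.

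**3. T-test at an assumed effect of d = 0.5 SD.** Noncentrality = d × √(n/2) = 0.5 × √17.5 = 2.092, with 68 df and critical value 1.995. Power is 54.1%.

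**4. ANCOVA on one baseline.** With usable correlation r between baseline and week-1 headache, noncentrality = 2.092 / √[(1 − r²)(1 + 1/66)], with 67 df and critical value 1.996. The factor 1 + 1/66 charges for fitting the covariate.

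**5. Recall error.** A single recalled answer is a noisy baseline. If its reliability is R, then usable r = true r × √R. For example, 0.5 × √0.7 = 0.418.

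| True correlation | Reliability | Usable r | ANCOVA power | Change from 54.1% |
|---|---|---|---|---|
| 0 | – | 0 | 53.4% | −0.7 points |
| 0.3 | 0.5 | 0.21 | 55.3% | about +1 |
| 0.3 | 0.7 | 0.25 | 56.1% | +2 |
| 0.5 | 0.5 | 0.35 | 59.0% | about +5 |
| 0.5 | 0.7 | 0.42 | 61.5% | about +7 |
| Usable r taken directly | – | 0.3 | 57.3% | about +3 |
| Usable r taken directly | – | 0.5 | 65.6% | about +12 |
| Usable r taken directly | – | 0.7 | 81.7% | about +28 |

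Power equals the t-test's at usable r = 0.124. The last three rows correspond to t-tests with 37.8, 45.6 and 66.6 per group.

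**6. Simulation check.** With 70 subjects allocated by coin toss and 12,000 runs per setting, the t-test gave 0.53-0.54 and ANCOVA gave 0.568, 0.649 and 0.816 at r = 0.3, 0.5 and 0.7. Type I error was 0.046-0.049 for the t-test and 0.047-0.048 for ANCOVA. With values rounded and bounded to 0-7 (underlying mean 4, SD 2), the t-test gave 0.52 and ANCOVA 0.55, 0.62 and 0.77. Those bounded values resemble headache days; a skewed attack count was not simulated.

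**The case against.** The strongest reply is that nothing here is an error. Randomisation makes the unadjusted t-test valid, the trial is sized on pain, that calculation reproduces, and the pain comparison is untouched. This stands in full.

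A reader might go further and infer that, without a baseline, the headache comparison is biased or its error rate inflated. The documents do not support that. With 35 per group the standard error of a baseline mean difference is √(2/35) = 0.239 SD, so the arms will differ by more than 0.25 SD in usual headache frequency about 30% of the time. But the t-test's standard error already reflects such chance imbalance. It is the same loss of precision seen from another side, not an additional harm.

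A second objection is that the gain is not assured. This also stands. No correlation, reliability, headache SD or headache effect is given. The hypothesis concerns attacks related to procedure pain, and nothing in the documents shows that the preceding week's frequency predicts these. For an assumed 0.3 SD effect, power is 24% by t-test and 25-29% by ANCOVA at r = 0.3-0.5, which is low either way.

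Third, the unseen diary form may already ask about earlier headache, and Section IV's frequency item has no time point. So it can be said only that no baseline is described, not that none is collected. Even then, the planned t-test would not use it.

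Fourth, diaries come back by mail, and unreturned ones may be the larger loss. At an assumed 28 returns per arm, power for 0.5 SD is 45% by t-test, and 48% or 56% by ANCOVA at r = 0.3 or 0.5. Adjustment does not replace missing outcomes.

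**Conclusion.** The point holds as an inexpensive improvement to the second hypothesis, not as a flaw in the trial's validity. The plan describes no pre-injection headache measure and names only unadjusted t-tests.

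With a recalled baseline, the realistic gain for a 0.5 SD effect is about 1 to 7 points, from 54% to 55-62%. Gains to 66% or 82% require a usable correlation of 0.5 or 0.7, which a single recall question may not reach. The worst case, at zero correlation, is a loss of under 1 point.

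All of this rests on assumed effect, correlation and reliability values and on roughly normal outcomes; the gain for a skewed attack count may be smaller. It would be wrong to read the result as a promise of added power, or as a reason to change N = 70.

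**What to change.** 1. **Sections III.D and IV.** At the existing diary session, before injection, each subject writes on the form the headache frequency of the preceding 7 days, in the same unit the diary uses. Allocation has already happened by then and the text does not say who runs the session. The wording should therefore be fixed and the blinded subject should answer unaided, because the randomising investigators know the assignment.
2. **Section V.** Compare week-1 headache frequency by ANCOVA on treatment and that baseline, two-sided .05, in place of the unadjusted t-test. Fill a missing baseline with the overall mean, so that a subject with a returned diary is not dropped for lack of it. This does nothing for diaries that are not returned.

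N = 70 and the pain t-test stay. The change should not make the headache test conditional on a significant pain result. With pain power of 90.2% and outcomes assumed independent, that would give about 0.902 × 57.3% = 51.7% at r = 0.3, below the present 54.1%.

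The cost is one written question at a session already planned and a few sentences in three sections, with no extra subjects or visits.

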#### **C. Study Population**

- Patients with diagnosis of chronic migraine receiving FDA-approved treatment with BoNTA injection as per standard protocol used in PREEMPT study [2]. Standard protocol consists of 31 injection sites, with total dose ranging from 155 u to 195u.
- Exclusion criteria:
  1. Age < 18, or > 79
  2. Subjects whom BoNTA injections deviate from standard protocol for any reason, such as head/neck infection, head deformity, recent surgery...etc.
- Study population will be randomized into two groups; preserved saline and preservative-free saline

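### Does the second hypothesis need a stated unit and counting rule for headache attacks in the week after injection?

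*Combined protocol and SAP*

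**What the plan says.** Section II states two hypotheses. The first is about procedure pain. The second is that reducing that pain "will also result in reduced migraine/headache attacks in the week immediately following the procedure". Section I supplies the mechanism: "the pain during procedure is a known migraine trigger for many of these patients". It also cites a study in which "up to 5% report migraine attacks lasting more than 5 days as a side effect of BoNTA injection".

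Section III.D gives the source of the data: "They will be asked to maintain a 7-day headache diary (see supplementary"). Each subject also gets a 10 to 15 minute session on how to use the diary. The form itself is not in the text available for this review.

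Section IV lists the item collected as "headache/migraine frequency and use of headache symptomatic medications". Section V says "T-tests will be used to compare outcome of both groups" and bases the sample size on the verbal pain score alone.

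The exclusions in Section III.C are age and "Subjects whom BoNTA injections deviate from standard protocol for any reason". A headache on the day of injection is not mentioned there, and the Section IV list has no item for it.

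**The concern.** Three words stand for the second outcome: attacks in Section II, frequency in Section IV and outcome in Section V. None comes with a rule for where one attack ends and the next begins. In chronic migraine over a seven-day window this can matter. A headache on six consecutive days is one attack but six headache days.

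A headache already under way at injection raises a second question. Injection pain cannot have triggered it, yet it may appear in the diary. If headache status at injection was not recorded, it cannot be recovered later.

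At stake is selective reporting. If the measure is still open when the diaries are read, the second hypothesis could be called supported on whichever measure is significant. That would raise the false-positive rate of that test.

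**Working it through.** **The plan's own figure.** Section V gives a difference of 1.5, SD 1.9, alpha 0.05 and 90% power. The normal approximation for a two-sided test is n per group = 2 × (1.96 + 1.2816)² × (1.9/1.5)² = 2 × 10.51 × 1.604 = 33.7, so 34. The noncentral t calculation gives 34.7, so 35 per group and 70 in total, as stated, with power of 90.2%. A one-sided test would need only 28 per group, so the plan's test is taken as two-sided. None of this involves the diary.

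**Inputs for the second hypothesis.** From the plan: 35 per arm, seven diary days, t-test at 0.05. The plan gives no headache rates, so these are assumptions:

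- probability of headache on day 1: 0.60
- probability that a headache starts after a headache-free day: 0.35
- probability that a headache persists to the next day: 0.60
- an attack is an unbroken run of headache days

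The base model was run for 40,000 simulated trials.

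**No true effect, two measures.**

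| Event | Probability |
|---|---|
| Attack count significant in favour of preserved saline | 2.5% |
| Headache days significant in favour | 2.3% |
| Either significant in favour | 4.5% |
| Either significant, in either direction | 9.3% |

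By symmetry the favourable figure should be about half the last row, 9.3/2 = 4.65%, which agrees with 4.5% within simulation error. The ceiling for two measures is 2 × 2.5% = 5% in favour, or 2 × 5% = 10% in either direction. Over 27 combinations of assumed rates (headache at injection 0.3 to 0.7, onset 0.20 to 0.50, persistence 0.4 to 0.8), the either-direction figure was 7.9% to 10.0%.

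The hypothesis predicts a reduction, so the favourable row is the relevant one. The 9.3% includes trials that would contradict the hypothesis.

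**Four definitions.** Suppose it is also open whether a headache under way at injection counts. The either-direction figure is then 11.4% to 16.4%, or about 5.7% to 8.2% in favour after halving. This requires the best of four results to be reported.

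**Do the two measures disagree when there is an effect?** Base model, significant in favour:

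| Assumed effect | Count | Days | Exactly one | Exactly one if independent |
|---|---|---|---|---|
| Onset 0.35 to 0.25 | 24.8% | 18.0% | 26.8% | 33.9% |
| Day 1 0.60 to 0.40 | 9.2% | 9.8% | 14.7% | 17.2% |
| Both | 51.1% | 42.4% | 36.8% | 50.2% |

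The last column is a(1 − b) + b(1 − a). In the first row this is 0.248 × 0.820 + 0.180 × 0.752 = 0.339. Disagreement is common because power is low: at these power levels two imperfectly correlated tests will often split. Average power differs by at most about 9 points (51.1 − 42.4 = 8.7).

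**Headache under way at injection.** Counting it adds prevalence × persistence attacks per patient, from 0.3 × 0.4 = 0.12 to 0.7 × 0.8 = 0.56. Under the trigger mechanism in Section I, randomisation gives both arms the same expected addition. It adds noise, not a difference between arms.

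**The case for a change.** The strongest case for a change is that this is one of only two stated hypotheses and that a few sentences would settle it. A diary form may fix what patients record without fixing what is analysed, since daily entries can yield either attacks or days. Blinding in Section III.D covers the injectors and the subject; the plan does not say whether the analyst is blinded. Free choice between two measures roughly doubles the false-positive rate of this test, and among four it does more.

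Part of this stands. The visible text has no attack-boundary rule and no rule for a headache present at injection, and the relative doubling is correct arithmetic. What does not follow is that the plan is defective:

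- Section II names attacks and fixes a one-week window, and Section IV's frequency fits that reading. Headache days is an alternative brought in from outside the text.
- The form to which Section III.D refers cannot be counted as absent because it is not in the text reviewed. The training session suggests that recording rules were meant to exist.
- The inflation is a property of choosing after the fact, not of any measure the plan would use. Nothing in the documents points to such a choice, and if the diary fixes the unit and rule the inflation is zero.
- The units would diverge systematically if preserved saline shortened attacks, which the plan does not propose.

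**Conclusion.** The gap in the visible text is real but narrow: a counting rule, not an outcome. An analyst can fill it in more than one sensible way, and each gives a valid comparison of randomised groups at the nominal level. Writing down a unit would record a choice without improving the method, and neither unit is clearly better. The count has slightly more power in most of the assumed trigger scenarios, while days would pick up a shortening of attacks.

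At worst, reporting the better of attack count and headache days moves the chance of falsely claiming support from about 2.5% to about 4.5% in the base case. Picking the best of four definitions would move it to roughly 5.7% to 8.2%. All these figures rest on assumed headache rates and on deliberate selection. They concern a hypothesis on which the sample size was not based, and the 70-patient pain-score comparison is unaffected. No change to the plan follows.

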### **III. METHODS**

#### **A. Study Design**

The study is a prospective, randomized, double-blind trial.

Subjects will be enrolled consecutively at UHCC headache clinic from the practice of the two lead authors; AZ and LM who will be performing the injections.

Two of the investigators, SH or AF, will perform the randomization through simulated, web-generated, coin toss.

#### **B. Study Materials**

Our preservative-free saline is a 0.9% sodium chloride injection. Each milliliter contained 9 mg of sodium chloride. The solution is supplied in 25-mL, single-dose vials.

Our preservative-containing saline is a bacteriostatic 0.9% sodium chloride injection. Each milliliter contained 9 mg of sodium chloride and 9 mg of benzyl alcohol added as a bacteriostatic preservative. The solution is also supplied in 25-mL, single-dose vials.

Both preserved saline and preservative-free saline are identical-appearing, colorless solutions.

BoNTA (Botox® Allergan Inc) is a powder vial containing 200 u. Powder is reconstituted with 4 ml of normal saline and then drawn in four 1 ml syringes. All four syringes are used in a single patient in one session.

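### Does using all four syringes in each patient conflict with the 155–195 U dose range and the 31 injection sites?

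*Combined protocol and SAP*

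**What the plan says.** Section III.B (Study Materials) describes the product and its preparation. Each vial holds 200 U of toxin, which is dissolved in 4 mL of saline and divided equally among four syringes. On their use the section states: "All four syringes are used in a single patient in one session".

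Section III.C (Study Population) describes the regimen: "Standard protocol consists of 31 injection sites, with total dose ranging from 155 u to 195u". It also excludes "Subjects whom BoNTA injections deviate from standard protocol for any reason", giving infection, deformity and recent surgery as examples. Section I (Background and Significance) has the same number of sites: "Injections are administered at 31 sites of the head and neck, and treatment is repeated every 3 months".

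Section IV (Data Collection) lists what is recorded: "Collected data will include age, gender, race, ethnicity, verbal pain rating scale, headache/migraine frequency and use of headache symptomatic medications". Units, volume and number of sites are not on the list. Section V (Data Analysis) sizes the trial on a "minimally significant mean difference in verbal pain score of 1.5" and compares the groups by t-test, with no covariates.

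**The concern.** The vial, the dilution and the syringe count together suggest 200 U per patient, which lies above the stated maximum of 195 U. If that were what happened, every subject would be outside the protocol's own range, and one might ask whether the exclusion for non-standard injections applied to all of them. A second worry is that a range of 155 to 195 U seems to call for more needle sticks at the top than at the bottom, while the number of sites is fixed at 31.

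The outcome is procedure pain, so injected volume and number of sticks could plausibly affect it. In the preserved-saline arm, volume also sets how much benzyl alcohol is given. If these quantities vary and are not recorded, a source of variation in the primary outcome can be neither seen nor compared between arms.

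**Working it through.** **Inputs.** Vial 200 U, diluent 4 mL, four syringes of 1 mL, and benzyl alcohol 9 mg/mL in the preserved saline (III.B). Range 155–195 U and 31 sites (III.C). Difference 1.5, SD 1.9, power 90%, alpha 0.05, 35 per group (V). Two-sided testing is assumed, because V does not state it.

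**1. The plan's own sample size.** The normal approximation is n = 2 × (1.960 + 1.282)² × (1.9/1.5)² = 2 × 10.51 × 1.604 = 33.7, or 34 per group. The t-test calculation gives 34.7, or 35 per group, with power 0.902 at 35. The stated 70 reproduces, and dose and volume do not enter it.

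**2. Dose against syringes.** Concentration = 200 U / 4 mL = 50 U/mL, and volume = dose / 50.

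| Total dose | Volume | Left of 4 mL | Per site (÷ 31) | Benzyl alcohol (× 9 mg/mL) |
|---|---|---|---|---|
| 155 U | 3.1 mL | 0.9 mL (45 U) | 5.0 U | 27.9 mg |
| 195 U | 3.9 mL | 0.1 mL (5 U) | 6.29 U | 35.1 mg |
| 200 U, if emptied | 4.0 mL | 0 | 6.45 U | 36.0 mg |

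Three syringes hold 3 mL, or 150 U, which is less than the lowest permitted dose. The fourth is therefore needed in every patient, and the III.B sentence is true across the whole III.C range if a remainder is left. A conflict arises only if *used* means emptied. It would then be 200 − 195 = 5 U, 0.1 mL and 36.0 − 35.1 = 0.9 mg of benzyl alcohol above the maximum.

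**3. Number of sites.** Sections I and III.C both give 31. A total of 155 to 195 U fits 31 sites at 5.0 to 6.29 U each. A count that rises to 195/5 = 39 needs a constant 5 U per site, which the protocol does not state.

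**4. How far arms could differ in dose by chance.** The SD of a quantity confined to 155–195 U is at most half the range, 20 U, reached when half the patients are at each end. With about 35 per arm, the standard error of the difference in mean dose is at most 20 × √(2/35) = 4.78 U. A 95% limit is 1.96 × 4.78 = 9.4 U, or 9.4/50 = 0.19 mL. This is a ceiling under an extreme assumption. The documents give no effect of dose or volume on pain, so it cannot be turned into pain points or lost power.

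**The case for a change.** The strongest argument for a change does not depend on what *used* means. Even with a remainder left, dose and volume may differ between patients by 195/155 − 1 = 26%, and none of this is on the data list. Allocation is an unstratified coin toss, so a chance imbalance could arise and go unseen. Nor does the protocol say that the dose is fixed before the first injection. If it were adjusted to how the patient tolerates the session, it could differ by arm despite blinding. Extra form fields would cost little.

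It stands that dose balance cannot be tabulated from the listed data and that III.B could have been worded more clearly. The rest does not support a change. Random allocation with injectors and patients blinded (III.A, III.D) makes dose variation a source of noise or chance imbalance. The t-test's standard error allows for both, since any scatter due to dose is part of the observed SD. If dose did respond to pain during the session, that would itself be an effect of the diluent. The comparison as allocated would still be valid, and adjusting for the dose given would be questionable. The number of sites would be useless as a covariate if it is 31 for everyone.

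The appeal to the exclusion criterion is also weak. Its examples concern patients who cannot have the standard injections, and nothing suggests that liquid left in a syringe was meant to trigger it.

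**Conclusion.** No change to the plan follows. The apparent contradiction rests on reading *used* as emptied, which the protocol never states; on the other reading III.B and III.C agree at every dose from 155 to 195 U. On the emptied reading the discrepancy is 5 U and 0.1 mL above the stated maximum, and the two sections would have to be reconciled by those responsible for the treatment. The documents do not settle which reading was meant, and no view is taken here on dose. There is no inconsistency in the number of sites.

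The missing dose and volume fields are an omission of descriptive detail. They do not affect the sample size or the validity of the primary comparison, and no gain in precision from recording them can be shown from the documents. This conclusion assumes that allocation and blinding work as described, and that any variation in dose within the range arises in both arms alike.
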